8.2. Protocol Deviations

Deviations from the CSP will be monitored throughout the conduct of the study. Rules and definitions are included within the study document [Study Deviation Rules.XLSX](#).

Significant protocol deviations will be summarized by number and percentage of participants. All protocol deviations will be listed. A separate listing for protocol deviations due to COVID-19 will be provided.

8.3. Demographic and Baseline Characteristics

The following demographic and baseline characteristic variables will be summarized:

- age and age category (< 30, ≥ 30 years),
- sex,
- ethnicity and race,
- height, weight, and body mass index at Screening,
- reported diagnosis of bronchiectasis,
- type of CFTR modulator (categories),
- type of antibiotics for stable CF treatment (inhaled, oral, nasal),
- use of pancreas enzymes,

- Pre-bronchodilator FEV₁ and ppFEV₁ at Baseline,
- NE, CatG, and PR3 range categories in sputum at Baseline.

The information about the bronchiectasis diagnosis will be obtained from the medical history eCRF, the type of antibiotics for stable CF treatment, and the use of pancreas enzymes from the concomitant medication eCRF reviewed and selected by Insmed.

8.4. Medical History

All medical history entries will be coded using Medical Dictionary for Regulatory Activities (MedDRA). Number and percentage of participants with medical history findings will be summarized by System Organ Class (SOC) and Preferred Term (PT).

Participants will be counted once in each SOC and in each PT.

8.5. Prior and Concomitant Medications and Procedures

Prior and concomitant medications will be coded using the World Health Organization (WHO) Drug dictionary.

The reported medication will be classified as ‘Prior only’, ‘Prior and concomitant’ or ‘Concomitant only’. These 3 categories are mutually exclusive:

- ‘Prior only’: if the participant has not taken any IP; or if the medication end date is before IP start date. If the medication end date is partially missing, the medication will only be assigned to ‘Prior only’ if the partial date gives clear evidence that the medication stopped before IP start.
- ‘Concomitant only’: if the medication start date is on or after IP start date. If the medication start date is partially missing, the medication will only be assigned to ‘Concomitant only’ if the partial date gives clear evidence that the medication started on or after IP start date.
- ‘Prior and concomitant’: if the medication start date is before IP start date and the medication end date is on or after IP start date. If the medication start date or end date are partially or completely missing, the medication will be assigned to ‘Prior and concomitant’ unless there is clear evidence that the medication stopped before IP start date (that is, the medication should be assigned to ‘Prior only’) or that the medication started after IP start date (that is, the medication should be assigned to ‘Concomitant only’).

Concomitant medications (i.e., medication classified as ‘Concomitant only’ or ‘Prior and concomitant’) will be summarized showing the number and percentage of participants taking concomitant medications by Anatomical Therapeutic Chemical (ATC) classification level 4 and PT within ATC4. If the ATC level 4 coding is not available for a PT, the next available lower-level ATC code will be used.

Non-pharmacological procedures will be listed but not summarized.

8.6. COVID-19 Impact

Potential COVID-19 impact is captured in the eCRF and will be summarized by participant.

Subject disposition summary and listing will include (see [Section 8.1](#)):

- Screen failure related to COVID-19
- Early termination of study related to COVID-19

AE overview table and listings will include (see [Section 10.2](#)):

- AEs that fall into the category of COVID-19 related

Summary table and listing of dose interruption will include (see [Section 10.1](#)):

- Dose interruption related to COVID-19

Summary and listing of protocol deviations will include (see [Section 8.2](#)):

- Protocol deviations due to COVID-19

Early termination of study related to COVID-19 will be determined using the AE eCRF form: if the question “was the AE COVID-19 related?” is answered with “yes” and this AE caused early termination of the study, this is considered early termination of the study related to COVID-19.

9. EFFICACY

For the general layout of the tables see [Section 7.1](#).

The primary and secondary endpoints are related to PK and Safety (AEs) (see [Section 11](#) and [Section 10.2](#)) and will be analyzed using the PK and Safety Analysis Sets, respectively. The efficacy in this study is exploratory and will be analyzed using the ITT Analysis Set.

For the exploratory endpoints related to PD, refer to [Section 12](#). Analysis will be based on the PD Analysis Set.

The strategies for ICEs as outlined in detail for the analysis of the endpoints related to spirometry and CFQ-R in [Section 3.3](#) and [Section 7.2](#) will be applied.

9.1. Spirometry

Spirometry tests include the following: prebronchodilator FEV₁, prebronchodilator ppFEV₁, FVC, and FEF_(25-75%).

Observed values and change from baseline at Day 28 will be summarized descriptively by scheduled visit. If applicable (more than 5 participants who prematurely discontinued the study) a separate analysis using the end of treatment (EoT) assessment, i.e., Day 28 or Early Discontinuation, will be done.

An analysis of covariance will be performed for change from baseline at Day 28 including the baseline value in the model as fixed covariate and the treatment group/dose level as fixed factor. The analysis will be stratified by CFTR modulator / non-modulator if sample sizes permit (see [Section 7.1](#)). Least Squares (LS) means for each treatment group and dose levels with 95% CIs and LS mean differences between each Brensocatib dose level and placebo with 95% CIs will be provided.

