4.2. Sample Size Determination

Overall, the study will initially enroll approximately 25 participants. The 10 mg, 25 mg, and 40mg arm will enroll approximately 7 participants each, and the placebo arm will enroll approximately 4 participants. For the active treatment arms, there will be 2 strata: approximately 5 participants who have previously received and will continue to receive CFTR modulators as concomitant medication and 2 participants who have either never previously received CFTR modulators or have not been administered CFTR modulators within 30 days prior to Screening (Visit 1) and will not receive CFTR modulators during the study (non-modulator stratum). For the placebo arm, approximately 3 participants will be randomized into the CFTR modulator stratum and 1 participant into the non-modulator stratum.

If there are no safety issues observed with the first 3 doses, an additional cohort will be similarly randomized: 7 participants (5 participants CFTR modulator and 2 participants non-modulator stratum) on active treatment with 65 mg and 2 participants on placebo (1 participant each in the CFTR modulator and non-modulator strata), increasing the sample size from approximately 25 to 34 participants.

A formal sample size calculation has not been performed. The number of participants has been chosen based on feasibility, as is typical and standard for such multiple ascending dose study designs and is considered sufficient to meet the study objectives.

Brensocatic AUC_{0-24} and C_{max} will be summarized by dose group and by dose group within each stratum (CFTR modulator and non-modulator) using the GM. The precision, as measured by the width of confidence intervals (CIs), for these GMs will depend on the observed variability and sample size. The following tables present descriptions of 95% CIs for a range of possible values of the geometric coefficient of variation percentage (gCV%) of the GM. [Table 2](#) presents participants treated with brensocatic per dose group (N=10 and N=7), and [Table 3](#) presents participants treated with brensocatic per stratum (N=5) (CFTR modulator) within dose group.

Table 2: 95% CIs for Values of Inter-Participant gCV% of the AUC_{0-24} and C_{max} GM in Each Actively Treated Cohort

N	gCV%	GM 95% CI LL	GM 95% CI UL
10	30	GM÷1.234	GM×1.234
	40	GM÷1.317	GM×1.317
	50	GM÷1.402	GM×1.402
7	30	GM÷1.312	GM×1.312
	40	GM÷1.428	GM×1.428
	50	GM÷1.548	GM×1.548

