7. GENERAL STATISTICAL CONSIDERATIONS

7.1. General

Tables and figures will be provided by treatment group/dose level (10 mg, 25 mg, 40 mg, and 65 mg [if conducted] QD brensocatic, pooled placebo except for PK output). If sample sizes permit, summaries will be further stratified by CFTR modulator and non-modulator.

Treatment arm/dose levels will be presented in this stratified analysis if the number of observations is ≥ 2 . If the assignment to a stratum differs between the randomization file and the eCRF, the randomization file will prevail. In the listings, CFTR modulator use will be indicated by + for participants on CFTR modulator and by - for the non-modulator stratum following the Subject Identifier. For tables in the demographic and safety sections, also a Total column will be presented.

Descriptive statistics for continuous variables will be calculated at scheduled visits (nominal timepoints for PK) and will include the number of participants in the treatment group/dose level of the respective analysis set (N in column header of the table), the number of non-missing- observations (n), the number of observations below limit of quantification (BLQ) for PK and PD tests, arithmetic mean, standard deviation (SD), median, minimum, and maximum. For brensocatic plasma concentrations, the GM with 95% CI and gCV%, for PK parameters (except for t_{\max} and t_{last}), and PD tests, the GM and gCV% will be reported in addition. The GM will be derived by calculating the arithmetic mean of the natural log-transformed observations and then back-transforming the mean by exponentiation. The gCV% will be calculated as: $100 \times \sqrt{\exp[\text{variance of the log-transformed values}] - 1}$. GM and gCV% will only be calculated for quantifiable values above 0. For t_{\max} and t_{last} , only n, median, minimum, and maximum will be presented. For PK parameters, no descriptive statistics will be calculated when fewer than three individual PK parameter values are available. Summaries of continuous variables other than plasma concentrations that have some values recorded using approximate values (e.g., $<$ or $>$) will use the numeric part of the value in calculations. Rules for plasma concentrations BLQ or missing are given in [Section 11](#).

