7.2. Analysis Methods for Estimands

This is a Phase 2a study. No formal hypothesis will be tested and there will not be a confirmatory treatment comparison.

The following ICEs have been identified for this study (see [Section 3](#)):

1. Early discontinuation from the randomized IP for any reason,
2. Not on stable CFTR modulators for participants on modulators,
3. Use of antibiotics during an acute event that could affect NSP levels.

The table below gives an overview which analysis set(s) and strategy to deal with related ICEs will be used for the Estimands.

Estimand	Analysis Set	Strategy for ICEs
Primary, Secondary, and Exploratory PK	PK Analysis Set	For the first ICE, While-on-Treatment strategy: data collected prior to the occurrence of the ICE, i.e., to discontinuation of IP, will be included in the analysis. For the second and third ICE, the Treatment Policy strategy will be used, i.e., all data will be included in the analysis.
Safety	Safety Analysis Set	For the first ICE, While-on-Treatment strategy: data collected prior to the occurrence of the ICE, i.e., to discontinuation of IP, will be included in the analysis. For the second and third ICE, the Treatment Policy strategy will be used, i.e., all data will be included in the analysis.
Exploratory PD	PD Analysis Set	For the first and the third ICE, While-on-Treatment strategy: data collected prior to the occurrence of the ICE, i.e., to discontinuation of IP or to the use of antibiotics with impact on NSP levels, will be included in the analysis.

		For the second ICE, the Treatment Policy strategy will be used, i.e., all data will be included in the analysis.
Exploratory Efficacy, Microbiology	ITT Analysis Set	For the first ICE, While-on-Treatment strategy: data collected prior to the occurrence of the ICE, i.e., to discontinuation of IP, will be included in the analysis. For the second and third ICE, the Treatment Policy strategy will be used, i.e., all data will be included in the analysis.

The While-on-Treatment strategy will be applied for the first ICE: data collected after discontinuation of IP will be excluded from the derivation of PK parameters and from statistical analysis for PK, safety, PD, and efficacy analysis.

The Treatment Policy strategy will be applied for the second ICE: data will be included in derivation of PK parameters and in the PK analysis irrespective of changes in CFTR modulator use.

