9.2. CFQ-R

The CFQ-R ([Appendix A](#)) is a disease-specific QoL measure with 9 QoL domains (Physical Functioning, Role Limitations, Vitality, Emotional State, Social Limitations, Body Image, Eating Disturbances, Treatment Burden, Health Perception) that assess the impact of CF on overall health, daily life, and perceived well-being. There are 3 symptom scales: weight, respiratory, and digestion. Scores range from 0 to 100, with higher scores indicating better health.

Observed values and change from baseline for the 9 QoL domains and the 3 symptom scales will be summarized descriptively by scheduled visit.

A repeated measurement model will be used for the analysis of change from baseline in CFQ-R respiratory symptom scale. The model will include the baseline value as a fixed covariate and the treatment group/dose level, visit, and treatment group/dose level-by-visit interaction as fixed factors. Given the small sample size in each dose level, estimation of a complex variance-covariance structure with many parameters will be untenable. Therefore, the variance-covariance structure will be compound symmetric with the robust sandwich variance estimator.

This analysis will be performed using the MIXED procedure in SAS. If sample sizes permit, the analysis may be stratified by CFTR modulator / non-modulator. LS means for each treatment group and dose levels with 95% CIs and LS mean differences between each Brensocatib dose level and placebo with 95% CIs will be provided. The analysis will only be provided if data allow for such an analysis.

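### CFTR stratum is a randomization factor but not a stated term in the exploratory spirometry and CFQ-R models, and the two-per-arm rule is too low a threshold for a non-modulator model

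*SAP*

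**What the plan says.** SAP 4.3 randomizes participants separately within the modulator and non-modulator strata.

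SAP 9.1 specifies an ANCOVA of the Day 28 change in each spirometry variable, "including the baseline value in the model as fixed covariate and the treatment group/dose level as fixed factor". Stratum is not among these terms. The next sentence reads "The analysis will be stratified by CFTR modulator / non-modulator if sample sizes permit" and refers to SAP 7.1. The output is described as follows: "LS mean differences between each Brensocatib dose level and placebo with 95% CIs will be provided".

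SAP 7.1 gives one number for stratified output: "Treatment arm/dose levels will be presented in this stratified analysis if the number of observations is ≥ 2".

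SAP 9.2 models the CFQ-R respiratory score with baseline, treatment, visit and treatment-by-visit terms, again without stratum. It adds: "If sample sizes permit, the analysis may be stratified by CFTR modulator / non-modulator". It also says the model is run only when the data allow.

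On numbers, SAP 4.2 plans 5 modulators and 2 non-modulators per active dose. For placebo, "approximately 3 participants will be randomized into the CFTR modulator stratum and 1 participant into the non-modulator stratum". If the 65 mg cohort runs, placebo gains one participant in each stratum.

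On status, SAP 7.2 states: "No formal hypothesis will be tested and there will not be a confirmatory treatment comparison".

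**The concern.** A factor used to stratify randomization normally belongs in the analysis model. Here the only stratification factor is missing from the stated terms of both efficacy models, with no reason given.

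What takes its place is a conditional stratified analysis. SAP 9.1 with SAP 7.1 is most naturally read as separate models within each stratum. SAP 11.1.3 supports that reading: for the PK power model it names a stratum covariate and separate analyses by stratum as two distinct options, and SAP 9.1 mentions no covariate.

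The rule of two per arm is reasonable for deciding which columns of a descriptive table to show. It says little about whether a model with several arm means and a baseline slope can give a useful interval. The SAP is stricter elsewhere: SAP 7.1 suppresses descriptive statistics for PK parameters below three values, and SAP 11.1.1 does the same for concentrations. At stake are a small and avoidable loss of precision in the overall model, and non-modulator intervals resting on pairs of participants.

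**Working it through.** **Inputs.** Cell counts come from SAP 4.2, SAP 4.3 and SAP Table 1.
- 25 participants: three active doses at 5 modulators + 2 non-modulators, placebo 3 + 1.
- 34 participants: four active doses at 5 + 2, placebo 4 + 2.
- Interval: two-sided 95% (SAP 9.1).
- The documents give no SD for change in FEV1 or ppFEV1, so widths are in residual SD units. Full follow-up is assumed.

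**The plan's own figures.** The SAP gives no precision figure for the efficacy models. The nearest are the geometric-mean CI factors in SAP Tables 2 and 3, from exp[t(0.975, n−1) × √ln(1+CV²) / √n]. For n = 5 and CV 30% this is exp(2.776 × 0.2936 / 2.236) = 1.440, as stated. All nine tabulated factors reproduce to three decimals. The SAP gives no factor for n = 2. The same formula there yields 13.98, 31.86 and 69.70 at CV 30, 40 and 50%.

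**Method for the ANCOVA.**
- Residual df = N − (number of arms + 1 baseline slope), less 1 more if stratum is a factor.
- Half-width for one dose minus placebo = t(0.975, df) × √(1/n_dose + 1/n_placebo) when baselines are balanced. For the within-stratum and no-stratum models this is the minimum.
- The median over 20,000 draws of a normal baseline covariate is given beside it.

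| Model | Arms (placebo last) | df | t | Half-width, balanced | Median |
|---|---|---|---|---|---|
| Non-modulator, 25 | 2/2/2/1 | 7−5 = 2 | 4.303 | 5.27 | 5.74 |
| Non-modulator, 34 | 2/2/2/2/2 | 10−6 = 4 | 2.776 | 2.78 | 2.92 |
| Modulator, 25 | 5/5/5/3 | 18−5 = 13 | 2.160 | 1.58 | 1.60 |
| Modulator, 34 | 5/5/5/5/4 | 24−6 = 18 | 2.101 | 1.41 | 1.43 |
| All, no stratum, 25 | 7/7/7/4 | 25−5 = 20 | 2.086 | 1.31 | 1.32 |
| All, with stratum, 25 | 7/7/7/4 | 25−6 = 19 | 2.093 | 1.31 | 1.33 |
| All, no stratum, 34 | 7/7/7/7/6 | 34−6 = 28 | 2.048 | 1.14 | 1.15 |
| All, with stratum, 34 | 7/7/7/7/6 | 34−7 = 27 | 2.052 | 1.14 | 1.15 |

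Example (non-modulator, 34): 2.776 × √(1/2 + 1/2) = 2.78. The balanced column for the models with stratum ignores the slight stratum imbalance between arms; the median column includes it.

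**Reading the table.**
- *25 participants.* Placebo has one non-modulator and fails the rule of two, so no contrast with placebo is shown. The first row is what a fit would give without that rule.
- *34 participants.* The rule is met and the model can be fitted, but on 4 df. If one placebo non-modulator has no value, the rule excludes placebo again (if fitted anyway: 3 df, 3.182 × √1.5 = 3.90).
- *Cost of adding stratum.* The t ratio is 2.093/2.086 = 1.003 at 25 and 2.052/2.048 = 1.002 at 34. The medians, 1.33 against 1.32 and 1.15 against 1.15, also differ by under 1%.

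**Bias from leaving stratum out.** A contrast shifts by the difference in modulator share times the stratum effect. The share is 5/7 = 71.4% on each active dose. On placebo it is 3/4 = 75.0% (25 participants) or 4/6 = 66.7% (34). The differences are −3.6 and +4.8 percentage points, so the shift is about 4 to 5% of any stratum effect.

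**CFQ-R.** Interval widths for the repeated-measures model were not calculated. The point there rests on the model terms and the same participant counts.

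**The case against.** A reader might infer that the plan promises non-modulator differences from placebo that its enrolment cannot deliver. The documents do not support that. Stratified output is conditional in SAP 9.1 and optional in SAP 9.2. The sentence on differences from placebo does not mention stratum. The spirometry and CFQ-R estimands in SAP 3.3 allow treatment means alone when a model cannot be estimated. At 25 participants the rule of two removes the contrast, which is a safeguard doing its job. At 34 the model is estimable, so it is uninformative, not impossible.

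Three further objections have force:
- SAP 7.1 states when arms are shown. It does not say that two per arm is enough to fit a model, and the separate sample-size condition leaves room to decline. That stands, but no other number is given, so the decision is left open.
- Stratified could mean stratum-adjusted. SAP 9.1 does not exclude this. If it was intended, the model terms should say so.
- Omitting stratum has no demonstrated cost. The documents give no stratum effect on change from baseline, the shift is small, and the widths are nearly equal when stratum has no effect. This stands, and it limits the severity. It does not argue against a term that is almost free.

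Over-reading is also restrained: efficacy is exploratory (SAP 9), SAP 7.3 rules out inferential conclusions, and neither the primary and secondary endpoints nor the listed Safety Review Committee data include these models.

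Finally, dropping every within-stratum model would go too far. The modulator-only ANCOVA, at about 1.6 or 1.4 SD, is usable.

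**Conclusion.** The point holds as a low-severity improvement. The only randomization stratum is absent from the stated terms of both efficacy models, and the only numeric threshold for stratified output is a presentation rule too low for model-based intervals. A non-modulator contrast with placebo is not presentable at 25 participants. At 34 it has a half-width of about 2.8 to 2.9 residual SD, against about 1.15 SD for the overall model with stratum included.

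This should not be read as a biased analysis. The expected shift is about 4 to 5% of any stratum effect, although that depends on the planned balance, and with 4 to 6 placebo participants a missing value can disturb it. The gain from adding the factor is mainly precision, and only if stratum is prognostic.

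The figures assume the planned cell counts, no dropout and a normal baseline covariate. They do not depend on the unknown SD.

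**What to change.** - In SAP 9.1, add CFTR stratum (modulator / non-modulator, as in the randomization file, which SAP 7.1 already makes decisive) as a fixed factor in the single ANCOVA on all participants. Take LS means and differences from placebo from that model.
- In SAP 9.2, add the same factor to the repeated-measures model, keeping the existing condition that the data allow it.
- Limit non-modulator efficacy output to descriptive summaries and listings.
- In SAP 7.1, state that two observations per arm governs descriptive presentation only and does not trigger model-based output.
- The modulator-stratum model may be kept as a supplementary analysis.

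The cost is a few lines of SAP wording and 1 df per model, with under 1% of interval width lost in the ANCOVA if stratum has no effect. No new data are needed.

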9.2. CFQ-R

The CFQ-R ([Appendix A](#)) is a disease-specific QoL measure with 9 QoL domains (Physical Functioning, Role Limitations, Vitality, Emotional State, Social Limitations, Body Image, Eating Disturbances, Treatment Burden, Health Perception) that assess the impact of CF on overall health, daily life, and perceived well-being. There are 3 symptom scales: weight, respiratory, and digestion. Scores range from 0 to 100, with higher scores indicating better health.

Observed values and change from baseline for the 9 QoL domains and the 3 symptom scales will be summarized descriptively by scheduled visit.

A repeated measurement model will be used for the analysis of change from baseline in CFQ-R respiratory symptom scale. The model will include the baseline value as a fixed covariate and the treatment group/dose level, visit, and treatment group/dose level-by-visit interaction as fixed factors. Given the small sample size in each dose level, estimation of a complex variance-covariance structure with many parameters will be untenable. Therefore, the variance-covariance structure will be compound symmetric with the robust sandwich variance estimator.

This analysis will be performed using the MIXED procedure in SAS. If sample sizes permit, the analysis may be stratified by CFTR modulator / non-modulator. LS means for each treatment group and dose levels with 95% CIs and LS mean differences between each Brensocatib dose level and placebo with 95% CIs will be provided. The analysis will only be provided if data allow for such an analysis.

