4. STUDY DESIGN

4.1. Summary of Study Design

This is a Phase 2a, single-blind, randomized, placebo-controlled, parallel-group, multiple-dose study to assess the PK, PD, and safety of brensocatib 10, 25, and 40 mg QD in participants with CF. Following review of PK and safety data by a SRC, and provided that the SRC deems it appropriate to administer the next dose, a cohort of participants will receive brensocatib 65 mg QD on the same schedule as the previous cohorts. A tablet formulation of brensocatib 65 mg is not yet available; therefore, participants assigned to the 65 mg dose cohort will receive 1 tablet of brensocatib 25 mg and 1 tablet of brensocatib 40 mg.

Overall, the study will enroll approximately 25 to 34 participants. The first three brensocatib arms (10 mg, 25 mg, and 40 mg QD) will enroll approximately 7 participants each, and the placebo arm will enroll approximately 4 participants. For the active treatment arms, there will be 2 strata: 5 participants who have previously received and will continue to receive CFTR modulators as concomitant medication (CFTR modulator stratum), and approximately 2 participants who have either never previously received CFTR modulators or have not been administered CFTR modulators within 30 days prior to Screening (Visit 1) and will not receive CFTR modulators during the study (non-modulator stratum). For the placebo arm, approximately 3 participants will be randomized into the CFTR modulator stratum and 1 participant in the non-modulator stratum.

Each dose group will enroll participants in a 5:1 ratio (active : placebo) for the CFTR modulator stratum. For the non-modulator stratum, approximately 6 participants will be randomized to receive active treatment (10 mg, 25 mg, or 40 mg brensocatib) and approximately 1 participant to placebo.

If there are no safety issues observed in the first 3 dose cohorts, a 65 mg dose cohort will be similarly randomized: 7 participants (5 participants CFTR modulator and 2 participants non-modulator stratum) in active treatment and 2 participants in placebo (1 participant each in the CFTR modulator and non-modulator strata), increasing the sample size from approximately 25 to 34 participants.

The overview below illustrates the prospective number of participants based on approximately 25 participants in the first 3 cohorts (10 mg, 25 mg, and 40 mg) and approximately 9 participants in the fourth cohort (65 mg).

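### The CFQ-R model pairs a sandwich variance, with no stated small-sample correction or degrees of freedom, with 4 to 6 placebo participants, so its nominal 95% intervals cover about 88 to 91%

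*SAP*

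**What the plan says.** SAP 9.2 models change from baseline in the CFQ-R respiratory scale. "The model will include the baseline value as a fixed covariate"; dose group, visit and their interaction are the fixed factors. The SAP argues that the small dose groups rule out a covariance structure with many parameters, and concludes that "the variance-covariance structure will be compound symmetric with the robust sandwich variance estimator". "This analysis will be performed using the MIXED procedure in SAS". The output is stated as "LS mean differences between each Brensocatib dose level and placebo with 95% CIs will be provided".

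The group sizes are in SAP 4.2: the three first dose arms have "approximately 7 participants each, and the placebo arm will enroll approximately 4 participants". The 65 mg cohort, if run, adds 7 active and 2 placebo participants. SAP 7.1 reports "pooled placebo except for PK output", so the comparator is 4 or 6 people.

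SAP 9.2 states neither a small-sample correction to the sandwich nor a denominator degrees-of-freedom method. The model is run only if the data allow, with no criterion given, and may be stratified by CFTR modulator use.

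**The concern.** A sandwich variance is justified when there are many independent participants. Here a separate mean is fitted for each arm at each visit, so each arm's contribution comes from that arm's own residuals, with divisor n instead of n-1. With 4 placebo participants the placebo part is about three quarters of its true size and rests on 3 degrees of freedom, while a between-within t quantile uses 20 or more.

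The SAP's small-sample argument supports compound symmetry, which needs few parameters. It does not support a variance estimator that depends on large numbers. What is at stake is the honesty of the reported intervals. No hypothesis is tested, so these CIs are the main statement of uncertainty for the CFQ-R comparisons with placebo.

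**Working it through.** **Plan's own figures.** The documents give no precision or coverage figure for CFQ-R. The nearest are the geometric-mean CI factors in SAP 4.2, which reproduce as exp[t(0.975, N-1) × √(ln(1+CV²)/N)]. For N = 7 and CV 30%: exp[2.447 × √(0.0862/7)] = 1.312, as printed. The SAP's own small-sample PK intervals thus use N-1 degrees of freedom.

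**Inputs.** From the SAP: 4 placebo with 7/7/7 active (N = 25), or 6 placebo with 7/7/7/7 active (N = 34); baseline, dose, visit and dose-by-visit effects; two-sided 95% CIs; Day 14 and Day 28 (SAP 3.3), with Day 35 also collected (protocol 1.3). Assumed, because not stated: classical sandwich, between-within degrees of freedom, complete data, normal errors, within-person correlation 0.3 to 0.7.

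**Hand check of the bias (no covariate).** The expected sandwich contribution of an arm is ((n-1)/n)/n against a true 1/n, in units of the residual variance.
- 4 placebo, 7 active: (0.75/4 + 0.857/7) / (1/4 + 1/7) = 0.310/0.393 = 0.79.
- 6 placebo, 7 active: (0.833/6 + 0.857/7) / (1/6 + 1/7) = 0.261/0.310 = 0.84.

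With the baseline covariate, simulation gives 76% and 82% of the model-based variance.

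**Simulated coverage when compound symmetry and equal arm variances hold** (6,000 to 8,000 runs per setting, Monte Carlo error 0.3 to 0.4 points; 2 or 3 visits; Day 28 and the average over visits):

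| Method | 4 placebo | 6 placebo |
|---|---|---|
| Classical sandwich, between-within df (20-21 or 28-29 with 2 visits) | 88.2-89.4% | 90.2-91.2% |
| Classical sandwich, normal quantile | 86.3-87.8% | 89.0-90.0% |
| Classical sandwich, placebo n-1 df | 97.1-97.7% | 95.4-96.4% |

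Over both sizes, a bias-reduced sandwich (CR2) with unchanged df covers 91.8-93.7%, a jackknife-type sandwich (CR3) 94.8-95.8%, and model-based compound symmetry 94.5-95.6%. The chance that a classical-sandwich interval wrongly excludes zero is therefore about 9 to 12% instead of 5% (100 - 91.2 = 8.8; 100 - 88.2 = 11.8).

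The result barely depends on the correlation or the number of visits. Skewed errors with 4 placebo give about 89%. With 3 evaluable placebo, coverage is about 86%. Stratifying by modulator use gives about 86% (3 placebo, 5/5/5 active) or 88 to 89% (4 placebo, 5/5/5/5 active).

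**When variances differ** (3,000 runs per setting, error about √(0.89 × 0.11/3000) = 0.6 points; 2 visits, correlation 0.5, Day 28; the SD ratios are assumptions):

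| Departure | Placebo n | Classical sandwich | Model-based CS |
|---|---|---|---|
| Day 28 SD 1.5 × Day 14 | 4 / 6 | 89.2 / 91.2% | 90.9 / 91.7% |
| Day 28 SD 2 × Day 14 | 4 / 6 | 89.0 / 91.8% | 88.6 / 89.0% |
| Placebo SD 2 × active | 4 / 6 | 84.8 / 89.9% | 83.6 / 86.8% |
| Both ratios 1.5 | 4 / 6 | 87.6 / 90.0% | 83.2 / 85.2% |

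A CR3 sandwich kept 93.6 to 95.3% in every setting of the check that covered equal and unequal variances.

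**The case against.** The strongest reply is that the sandwich has a purpose here. Compound symmetry is a simple working structure, and a robust variance insures against its being wrong. That stands. A reader might infer that the SAP should drop the sandwich and use model-based compound symmetry, which covers 95% when its assumptions hold. The second table does not support this: model-based coverage falls to between about 83 and 92% when visit or arm variances differ, and 4 to 6 placebo participants are too few to show which case applies. Heterogeneous compound symmetry deals with unequal visits but not unequal arms.

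A second reply is that the SAP does not exclude a correction, and that the same sandwich with placebo n-1 degrees of freedom would cover about 97% with 4 placebo. That is also fair: uncorrected is inferred from the SAP's silence. But the text names only the sandwich and MIXED, and a correction to the variance alone is not enough, since CR2 with unchanged degrees of freedom stays below 94%.

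A third is that the consequence is small. SAP 9 calls efficacy exploratory, SAP 7.3 rules out inferential conclusions, and the model is conditional on the data. This stands and sets the priority. A reader might also infer that too-narrow CFQ-R intervals would steer later trials. Protocol 2.2 instead names safety, PK and PK-PD relationships as the basis for dose selection, and the CFQ-R exposure-response work belongs to a separate plan (SAP 11.1.4).

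**Conclusion.** The point holds as a low-priority correction. As written, SAP 9.2 gives intervals labelled 95% that cover about 88 to 89% with 4 placebo participants and 90 to 91% with 6. This assumes the classical sandwich, between-within degrees of freedom and complete data; a normal quantile gives about 86 to 90%. The direction of the bias follows from the estimator and the arm sizes; the exact figure depends on the unstated degrees-of-freedom method.

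The documents do not support two wider readings: that the sandwich is worse than plain model-based compound symmetry in general, or that the PD analysis shares the fault. SAP 12 is descriptive and specifies no repeated-measures model.

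**What to change.** In SAP 9.2, replace the classical sandwich with a small-sample bias-corrected one: either a jackknife (CR3-type) form, or CR2 with matching Satterthwaite-type degrees of freedom. Name the degrees-of-freedom method, and name a SAS procedure that offers the chosen correction. Report REML model-based standard errors with Kenward-Roger degrees of freedom, using compound symmetry with variances that differ by visit, as a sensitivity analysis.

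The cost is a sentence or two in the SAP, a procedure option and one extra table. Intervals become wider, by roughly 10 to 20% in most cases. Where compound symmetry holds, the classical sandwich width is 0.87 to 0.90 of the model-based width, so the latter is 11 to 15% wider (1/0.90 to 1/0.87). For the jackknife form the arm contribution becomes (n/(n-1))/n, so without the covariate the width ratio to the classical sandwich is √(0.500/0.310) = 1.27 with 4 placebo and √(0.367/0.261) = 1.19 with 6. No change to data collection or design is needed.
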